11.1. Renal Insufficiency Analysis

The purpose of this analysis is to characterize the effect of renal impairment on the safety, and tolerability of simufilam.

Participants will be categorized into normal renal function or renal impairment groups based on their estimated glomerular filtration rate (eGFR) as shown in the table below.

Table 4: Renal Function Categories by eGFR Ranges

Renal Impairment ^a	Estimated eGFR (mL/min)
None (Normal)	≥ 90
Mild Renal Impairment	60 - 89
Moderate renal impairment	≥30 to <60
Severe Renal Impairment	≥15 to <30

- a. Stages of renal impairment are based on Chronic Kidney Disease Epidemiology Collaboration (CKD-EPI) equation (2021) – for Adult Participants (≥ 18 years)

11.1.1 Calculation of eGFR:

The eGFR (in mL/min) will be calculated using the Chronic Kidney Disease Epidemiology Collaboration (CKD-EPI) equation (2021) – for Adult Participants (≥ 18 years):

$$eGFR = 142 \times [\min(S_{Cr}/k, 1)]^\alpha \times [\max(S_{Cr}/k, 1)]^{-1.200} \times 0.9938^{Age} \times 1.012 \text{ (if female)}$$

where

S_{Cr} = standardized serum creatinine in mg/dL

$k = 0.7$ for females or 0.9 for males

$\alpha = -0.241$ for females or -0.302 for males

$\min(S_{Cr}/k, 1)$ is the minimum value of S_{Cr}/k or 1.0

$\max(S_{Cr}/k, 1)$ is the maximum value of S_{Cr}/k or 1.0

age in years

As the Creatinine is collected at the visits; Day 1 (Baseline), Week 4, Week 16, Week 40, and Week 52, eGFR will be calculated at the same visits.

11.1.2 Statistical Methods and Analysis

11.1.2.1 Statistical Summaries on Creatinine, eGFR and Renal Function

The descriptive statistics of the observed and the change from baseline in Creatinine will be summarized by treatment group and renal function through Week 52. The same information will be graphically displayed using a clustered bar chart.

The descriptive summary statistics of eGFR will be presented by treatment group and renal function through Week 52.

The number of participants and percentages of renal function will be presented for the subgroups; MMSE (16-20, 21-27), age (≥ 75 , 65-74, and < 65), sex, and ethnicity, by treatment group at Baseline (Day 1).

11.1.2.2 Statistical Summaries on Select TEAEs vs Renal Function at Baseline (Day 1)

The effect of renal impairment on TEAEs will be characterized by displaying the summary statistics as well as the plots.

A summary of TEAEs by relatedness and renal function derived at Baseline (Day 1) will be provided by treatment groups.

A summary of select TEAEs Incidence by Renal Function derived at Baseline (Day 1) will be provided along with a clustered bar plot, where the select TEAEs of interest (Preferred Terms of the 10 most frequent TEAEs at the end of the study) when assessing the impact of study drug according to renal function.

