14.3.1 Displays of Adverse Events		
14.3.1.1	Safety	Overall Summary of Treatment Emergent Adverse Events
14.3.1.2	Safety	Summary of Treatment Emergent Adverse Events by System Organ Class and Preferred Term
14.3.1.3	Safety	Summary of Treatment Emergent Drug-Related Adverse Events by System Organ Class and Preferred Term
14.3.1.4	Safety	Summary of Treatment Emergent Adverse Events by System Organ Class, Preferred Term, and Maximum Severity
14.3.1.5	Safety	Summary of Serious Treatment Emergent Adverse Events by System Organ Class and Preferred Term
14.3.1.6	Safety	Summary of Treatment Emergent Adverse Events Leading to Study Discontinuation by System Organ Class and Preferred Term

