14.3.5 Other Data Summary Tables		
14.5.1.1	Safety	Summary of Creatinine (umol/L) by Renal Function by Visit
14.5.1.2	Safety	Summary of eGFR (mL/min) by Renal Function by Visit
14.5.1.3	Safety	Summary of Renal Function by Subgroups at Baseline
14.5.2.1	Safety	Summary of TEAEs by Relatedness by Renal Function
14.5.2.2	Safety	Summary of Select TEAEs by Renal Function

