16.2.7 Adverse Event Listings	
16.2.7.1	Treatment Emergent Adverse Events
16.2.7.2.	Select Treatment Emergent Adverse Events Used for Renal Function

Data Listing Number	Table Title/Summary

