13.5. Planned Figure Descriptions

The following are planned summary figures for protocol number PTI-125-07. The figure numbers and page numbers are place holders only and will be determined when the figures are produced.

Table 9: Planned Figures

Figure Number	Population	Figure Title/Summary
14.6.1.1	Safety	Plot of Creatine (umol/L) Changes from Baseline by Renal Function and Treatment at Each Post-Baseline Visit
14.6.1.2	Safety	Plot of eGFR (mL/min) Changes from Baseline by Renal Function

		and Treatment at Each Post-Baseline Visit
14.6.2.1	Safety	Plot of Drug-Related TEAEs by Renal Function and Treatment
14.6.2.2	Safety	Plot of Select TEAEs by Renal Function and Treatment
Efficacy		
14.2.1	ITT	Summary of Primary, Secondary, and Exploratory Endpoints- Primary Efficacy model
14.2.2.1.1	ITT	Summary of Change from Baseline to Week 52 in ADAS-Cog12 Total Score By Visit and Treatment
14.2.2.1.2	ITT	Summary of Change from Baseline to Week 52 in ADAS-Cog12 Total Score By Visit and Treatment: Responder Analysis
14.2.2.1.3	ITT	Summary of Change from Baseline to Week 52 in ADAS-Cog12 Total Score By Visit and Treatment: Time Component Test
14.2.2.2	ITT-mild	Summary of Change from Baseline to Week 52 in ADAS-Cog12 Total Score By Visit and Treatment
14.2.2.3	ITT	Summary of Change from Baseline to Week 52 in ADAS-Cog12 Total Score By Visit and Treatment: Imputation Missing Not at Random
14.2.2.4.1	ITT	Summary of Change from Baseline to Week 52 in ADAS-Cog12 Total Score By Visit and Treatment Stratified by Mild (21- 27)/Moderate (<21) AD Status
14.2.2.4.2	ITT	Summary of Change from Baseline to Week 52 in ADAS-Cog12 Total Score By Visit and Treatment Stratified by Mild (21- 27)/Moderate (<21) AD Status: Responder Analysis
14.2.2.4.3	ITT	Summary of Change from Baseline to Week 52 in ADAS-Cog12 Total Score By Visit and Treatment Stratified by Mild (21- 27)/Moderate (<21) AD Status: Time Component Test
14.2.2.5.1	ITT	Summary of Change from Baseline to Week 52 in ADAS-Cog12 Total Score By Visit and Treatment Stratified by Mild (20- 27)/Moderate (<20) AD Status
14.2.2.5.2	ITT	Summary of Change from Baseline to Week 52 in ADAS-Cog12 Total Score By Visit and Treatment Stratified by Mild (20- 27)/Moderate (<20) AD Status : Responder Analysis
14.2.2.6	ITT	Summary of Change from Baseline to Week 52 in ADAS-Cog12 Total Score By Visit and Treatment Stratified by Age

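### The only renal-function summary described at preferred-term level is limited to the 10 most frequent TEAEs, so an uncommon event concentrated in renally impaired simufilam participants is unlikely to appear in it

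*SAP*

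**What the plan says.** SAP 11.1 gives the aim: "The purpose of this analysis is to characterize the effect of renal impairment on the safety, and tolerability of simufilam". Its Table 4 grades renal function by eGFR: normal at 90 or above, mild impairment 60 to 89, moderate 30 to below 60, severe 15 to below 30.

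SAP 11.1.2.2 plans two adverse-event summaries by baseline renal function.

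- The first covers TEAEs in general: "A summary of TEAEs by relatedness and renal function derived at Baseline (Day 1) will be provided by treatment groups". It corresponds to Table 14.5.2.1, "Summary of TEAEs by Relatedness by Renal Function", and to Figure 14.6.2.1, "Plot of Drug-Related TEAEs by Renal Function and Treatment". Neither is limited to ten terms, and neither is described as broken down by system organ class or preferred term.
- The second gives the incidence of selected events, defined as "Preferred Terms of the 10 most frequent TEAEs at the end of the study". It corresponds to Table 14.5.2.2, "Summary of Select TEAEs by Renal Function", Figure 14.6.2.2 and Listing 16.2.7.2, "Select Treatment Emergent Adverse Events Used for Renal Function". The basis of the ranking is not stated.

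Elsewhere, Table 14.3.1.2, "Summary of Treatment Emergent Adverse Events by System Organ Class and Preferred Term", shows every term, but no renal split is stated. The tables of serious TEAEs (14.3.1.5) and of TEAEs leading to study discontinuation (14.3.1.6) have no stated renal split either.

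**The concern.** The renal analysis is meant to show whether simufilam is tolerated differently when renal function is reduced. The events that matter most for that question are those whose excess on simufilam is larger in impaired participants. Choosing events by how common they are does not look for this. In participants aged 50 to 87 followed for a year, the ten most frequent terms will mostly be common background events, whether or not they relate to drug or kidney.

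An event confined to a small cell is diluted by everyone outside it. If it misses the ten, its renal pattern can be seen only within totals by relatedness, where common events dominate, and Figure 14.6.2.1 counts it only if the investigator called it drug-related. Serious events and discontinuations, which carry most weight in a tolerability conclusion, are not tabulated by renal function at all. At stake is a supplementary safety conclusion. The primary efficacy inference is not touched.

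**Working it through.** The plan gives no figure on this point to reproduce: no TEAE rates, no share of participants with impairment, and no frequency for the tenth-ranked term. What follows is an illustration.

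**Input from the documents.** 804 randomised (SAP 2.2), allocated 1:1, so about 402 per arm.

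**Assumptions.** *f* is the share with eGFR below 60 (the SAP's moderate and severe grades), *r0* the event rate everywhere except the impaired simufilam cell, *r1* the rate in that cell, and *c* the overall frequency of the tenth-ranked term.

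**Step 1: dilution.** Half of the impaired share is on simufilam, so overall incidence = *r0* + 0.5 × *f* × (*r1* − *r0*).

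- *f* = 20%, *r0* = 1%, *r1* = 10%: 0.01 + 0.10 × 0.09 = 1.9%. The cell holds 804 × 0.20 / 2 = 80.4 participants with about 8 events.
- *f* = 30%, *r0* = 1%, *r1* = 20%: 0.01 + 0.15 × 0.19 = 3.85%.

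**Step 2: chance of reaching the list.** Take *c* = 3%, about 24 of 804, and treat the total count as binomial.

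- At 1.9% overall, P(at least 24) is about 2%.
- At 3.85% overall, P(at least 24) is about 92%. It falls to about 45% if the cut-off is 32 (4%) and to about 6% if it is 40 (5%).

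In the first case, a 10% versus 1% comparison with about 80 per arm in the impaired stratum would have roughly 71% power at two-sided 0.05. The SAP plans no such test; the figure only shows that the data would carry information that the display omits.

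**Step 3: rate needed to reach the list.** Solving for the cell rate gives *r1* = *r0* + 2 × (*c* − *r0*) / *f*. With *r0* = 1%:

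| Share *f* | *c* = 3% | *c* = 5% |
|---|---|---|
| 10% | 41% | 81% |
| 20% | 21% | 41% |
| 30% | 14% | 28% |
| 60% | 8% | 14% |

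The 60% row stands for an event raised across all impaired grades, including mild, if these cover 60% of the sample (an assumption).

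**Step 4: other ranking bases.** If terms were ranked within the simufilam arm, the first example gives (8 + 0.01 × 322) / 402 = 11.22 / 402 = 2.8%, still under 3%. Ranking within renal category could bring the event in, but the SAP does not say that this is meant.

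**Step 5: age in the categories.** At the reference creatinine (0.9 mg/dL for men, 0.7 for women), the formula in SAP 11.1.1 crosses 90 at ln(142/90) / −ln(0.9938) = 73.3 years for men. For women, with 142 × 1.012 = 143.7, it crosses at ln(143.7/90) / −ln(0.9938) = 75.2 years. The categories therefore sort participants partly by age.

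**The case against.** A reader might infer that the ten terms are the only adverse events examined by renal function, or that a renally concentrated event is removed before it is tabulated. The documents do not support that. Table 14.5.2.1 covers TEAEs by relatedness and renal function for each arm, and Figure 14.6.2.1 covers all drug-related TEAEs, so such an event still counts in totals. Participant-level listings of adverse events, with separate ones for serious events, discontinuations and deaths, can be linked to renal function through Listing 16.2.8.6. The SAP Overview also allows further analyses if labelled exploratory. These points stand. What they do not supply is a planned display of individual events by renal function beyond the ten.

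It is equally tempting to say that such an event cannot reach the list. The figures above show that it can, and ranking on overall frequency is a reading, since the SAP leaves the basis open. The small-cell argument applies to moderate and severe impairment. Because the SAP also counts eGFR 60 to 89 as impairment, an event raised across all impaired grades would need a much lower rate to be listed.

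A third stronger reading is that any gradient across renal categories would be an age effect. Age does enter the formula, but the gradient is modest. One simulation assumed mean age 74 with SD 8, creatinine independent of age, 20% incidence at age 74, an odds ratio of 1.05 per year and no renal effect. It gave 17.6%, 21.4% and 22.3% in the normal, mild and moderate categories. At 5% incidence, under similar assumptions, the figures were about 4.4%, 5.5% and 5.7%. SAP 11.1.2.1 already tabulates renal function by age group, and Figure 14.6.2.2 shows both arms, so the placebo results would reveal a background gradient.

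Finally, SAP section 9 makes safety summaries descriptive unless otherwise specified. A small p-value for one chosen term would not be a missed finding under that plan.

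**Conclusion.** The point holds in a limited form. The SAP states a selection rule for its only preferred-term summary by renal function, and that rule is poorly matched to the purpose in SAP 11.1. An uncommon event concentrated in simufilam participants with eGFR below 60 would probably be missing from Table 14.5.2.2, Figure 14.6.2.2 and Listing 16.2.7.2, and would be seen by renal function only within the relatedness outputs. Serious TEAEs and TEAEs leading to discontinuation have no renal table.

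The size depends on assumptions that the documents cannot settle: the impaired share, the background rate and the tenth-rank frequency. With a 1% background and a cut-off of 3% to 5%, the impaired simufilam cell would need a rate of about 21% to 41% at a 20% share, or 14% to 28% at a 30% share, for expected overall incidence to reach the cut-off. The age issue is secondary and calls for caution in interpretation. This is a worthwhile improvement to a supplementary descriptive analysis and has no bearing on the co-primary results.

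**What to change.** Amend SAP 11.1.2.2 and the matching table, figure and listing as follows.

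- Keep the ten most frequent terms and state how they are ranked.
- Add every preferred term that meets a pre-set threshold in any treatment-by-baseline-renal-category cell, for example at least 5% and at least 3 participants. These values are a suggestion; the sponsor should fix its own before unblinding.
- Add rows for any serious TEAE and any TEAE leading to discontinuation.
- Within each renal category, show the simufilam minus placebo difference in incidence with a 95% CI, labelled descriptive.
- Note that each within-category difference compares randomised arms, but that comparing the differences across categories is not free of age, because age enters the eGFR formula.

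The cost is SAP wording and programming on data already collected: treatment, baseline eGFR and coded adverse events. The downside is a longer table in which some small-cell differences will arise by chance, which is why the descriptive label matters.

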13.1. Demographic Data Summary Tables and Figures

Table 5: Demographic Data Summary Tables and Figures

Table Number	Population	Table Title/Summary
14.1.1	All Subjects	Subject Disposition (Includes All Early Terminations)
14.1.2.1.1	ITT	Demographics and Baseline Characteristics
14.1.2.1.2	ITT-mild	Demographics and Baseline Characteristics
14.1.2.2	Safety	Demographics and Baseline Characteristics
14.1.2.3.1	ITT	Medical History

14.1.2.3.2	ITT-mild	Medical History
14.1.2.4.1.1	ITT	Prior Medications
14.1.2.4.1.2	ITT-mild	Prior Medications
14.1.3.1	Safety	Study Drug Exposure
14.1.3.2	Safety	Study Drug Compliance by Visit
14.1.4.1	ITT	Important Protocol Deviations
14.1.4.2	ITT-mild	Important Protocol Deviations

13.2. Efficacy Data

Table 6: Efficacy Data

Table Number	Population	Table Title/Summary
14.2.1	ITT	Summary of Primary, Secondary, and Exploratory Endpoints-Primary Efficacy model
14.2.2.1.1	ITT	Summary of Change from Baseline to Week 52 in ADAS-Cog12 Total Score by Visit and Treatment
14.2.2.1.2	ITT	Summary of Change from Baseline to Week 52 in ADAS-Cog12 Total Score By Visit and Treatment: Responder Analysis
14.2.2.1.3	ITT	Summary of Change from Baseline to Week 52 in ADAS-Cog12 Total Score By Visit and Treatment: Time Component Test
14.2.2.2	ITT-mild	Summary of Change from Baseline to Week 52 in ADAS-Cog12 Total Score By Visit and Treatment
14.2.2.3	ITT	Summary of Change from Baseline to Week 52 in ADAS-Cog12 Total Score By Visit and Treatment: Imputation Missing Not at Random
14.2.2.4.1	ITT	Summary of Change from Baseline to Week 52 in ADAS-Cog12 Total Score By Visit and Treatment Stratified by Mild (21-27)/Moderate (<21) AD Status
14.2.2.4.2	ITT	Summary of Change from Baseline to Week 52 in ADAS-Cog12 Total Score By Visit and Treatment Stratified by Mild (21-27)/Moderate (<21) AD Status: Responder Analysis
14.2.2.4.3	ITT	Summary of Change from Baseline to Week 52 in ADAS-Cog12 Total Score By Visit and Treatment Stratified by Mild (21-27)/Moderate (<21) AD Status: Time Component Test
14.2.2.5.1	ITT	Summary of Change from Baseline to Week 52 in ADAS-Cog12 Total Score By Visit and Treatment Stratified by Mild (20-27)/Moderate (<20) AD Status
14.2.2.5.2	ITT	Summary of Change from Baseline to Week 52 in ADAS-Cog12 Total Score By Visit and Treatment Stratified by Mild (20-27)/Moderate (<20) AD Status : Responder Analysis
14.2.2.6	ITT	Summary of Change from Baseline to Week 52 in ADAS-Cog12 Total Score By Visit and Treatment Stratified by Age
14.2.2.7	ITT	Summary of Change from Baseline to Week 52 in ADAS-Cog12 Total Score By Visit and Treatment Stratified by Gender
14.2.2.8	ITT	Summary of Change from Baseline to Week 52 in ADAS-Cog12 Total Score By Visit and Treatment Stratified by Ethnicity
14.2.2.9	ITT	Summary of Change from Baseline to Week 52 in ADAS-Cog12 Total Score By Visit and Treatment Stratified by Race

Table Number	Population	Table Title/Summary
14.2.2.10	ITT	Summary of Change from Baseline to Week 52 in ADAS-Cog12 Total Score By Visit and Treatment Stratified by ApoE Genotype
14.2.2.11	ITT	Summary of Change from Baseline to Week 52 in ADAS-Cog12 Total Score By Visit and Treatment Stratified by Baseline Cognitive Enhancer Status
14.2.3.1.1	ITT	Summary of Change from Baseline to Week 52 in ADCS-ADL Total Score By Visit and Treatment
14.2.3.1.2	ITT	Summary of Change from Baseline to Week 52 in ADCS-ADL Total Score By Visit and Treatment: Responder Analysis
14.2.3.1.3	ITT	Summary of Change from Baseline to Week 52 in ADCS-ADL Total Score By Visit and Treatment: Time Component Test
14.2.3.2	ITT-mild	Summary of Change from Baseline to Week 52 in ADCS-ADL Total Score By Visit and Treatment
14.2.3.3	ITT	Summary of Change from Baseline to Week 52 in ADCS-ADL Total Score By Visit and Treatment: Imputation Missing Not at Random
14.2.3.4.1	ITT	Summary of Change from Baseline to Week 52 in ADCS-ADL Total Score By Visit and Treatment Stratified by Mild (21-27)/Moderate (<21) AD Status
14.2.3.4.2	ITT	Summary of Change from Baseline to Week 52 in ADCS-ADL Total Score By Visit and Treatment Stratified by Mild (21-27)/Moderate (<21) AD Status : Responder Analysis
14.2.3.4.3	ITT	Summary of Change from Baseline to Week 52 in ADCS-ADL Total Score By Visit and Treatment Stratified by Mild (21-27)/Moderate (<21) AD Status : Time Component Test
14.2.3.5.1	ITT	Summary of Change from Baseline to Week 52 in ADCS-ADL Total Score By Visit and Treatment Stratified by Mild (20-27)/Moderate (<20) AD Status
14.2.3.5.2	ITT	Summary of Change from Baseline to Week 52 in ADCS-ADL Total Score By Visit and Treatment Stratified by Mild (20-27)/Moderate (<20) AD Status : Responder Analysis
14.2.3.6	ITT	Summary of Change from Baseline to Week 52 in ADCS-ADL Total Score By Visit and Treatment Stratified by Age
14.2.3.7	ITT	Summary of Change from Baseline to Week 52 in ADCS-ADL Total Score By Visit and Treatment Stratified by Gender
14.2.3.8	ITT	Summary of Change from Baseline to Week 52 in ADCS-ADL Total Score By Visit and Treatment Stratified by Ethnicity
14.2.3.9	ITT	Summary of Change from Baseline to Week 52 in ADCS-ADL Total Score By Visit and Treatment Stratified by Race
14.2.3.10	ITT	Summary of Change from Baseline to Week 52 in ADCS-ADL Total Score By Visit and Treatment Stratified by ApoE Genotype
14.2.3.11	ITT	Summary of Change from Baseline to Week 52 in ADCS-ADL Total Score By Visit and Treatment Stratified by Baseline Cognitive Enhancer Status
14.2.4.1	ITT	Summary of Change from Baseline to Week 52 in iADRS Total Score By Visit and Treatment
14.2.4.2	ITT-mild	Summary of Change from Baseline to Week 52 in iADRS Total Score By Visit and Treatment
14.2.4.3	ITT	Summary of Change from Baseline to Week 52 in iADRS Total Score By Visit and Treatment Stratified by Mild (21-27)/Moderate (<21) AD Status

Table Number	Population	Table Title/Summary
14.2.4.4	ITT	Summary of Change from Baseline to Week 52 in iADRS Total Score By Visit and Treatment Stratified by Mild (20-27)/Moderate (<20) AD Status
14.2.4.5	ITT	Summary of Change from Baseline to Week 52 in iADRS Total Score By Visit and Treatment Stratified by Age
14.2.4.6	ITT	Summary of Change from Baseline to Week 52 in iADRS Total Score By Visit and Treatment Stratified by Gender
14.2.4.7	ITT	Summary of Change from Baseline to Week 52 in iADRS Total Score By Visit and Treatment Stratified by Ethnicity
14.2.4.8	ITT	Summary of Change from Baseline to Week 52 in iADRS Total Score By Visit and Treatment Stratified by Race
14.2.4.9	ITT	Summary of Change from Baseline to Week 52 in iADRS Total Score By Visit and Treatment Stratified by ApoE Genotype
14.2.4.10	ITT	Summary of Change from Baseline to Week 52 in iADRS Total Score By Visit and Treatment Stratified by Baseline Cognitive Enhancer Status
14.2.5.1	ITT	Summary of Change from Baseline to Week 52 in MMSE Total Score By Visit and Treatment
14.2.5.2	ITT-mild	Summary of Change from Baseline to Week 52 in MMSE Total Score By Visit and Treatment
14.2.6.1	ITT	Summary of Change from Baseline to Week 52 in CDR-SB Total Score By Visit and Treatment
14.2.6.2	ITT-mild	Summary of Change from Baseline to Week 52 in CDR-SB Total Score By Visit and Treatment
14.2.7.1.1	ITT	Summary of Change from Baseline to Week 52 in NPI Total Score By Visit and Treatment
14.2.7.1.2	ITT	Summary of Change from Baseline to Week 52 in NPI Total Score By Visit and Treatment in Subgroup of Individuals with an NPI-10 Score ≥ 2
14.2.7.1.3	ITT	Summary of Change from Baseline to Week 52 in NPI Agitation and Aggression Domain Scores By Visit and Treatment in Subgroup of Individuals with a non-zero Domain Score at Baseline
14.2.7.1.4	ITT	Summary of Change from Baseline to Week 52 in NPI Total Score By Visit and Treatment: Responder Analysis
14.2.7.2.1	ITT-mild	Summary of Change from Baseline to Week 52 in NPI Total Score By Visit and Treatment
14.2.7.2.2	ITT	Summary of Change from Baseline to Week 52 in NPI Total Score By Visit and Treatment Stratified by Mild (21-27)/Moderate (<21) AD Status : Responder Analysis
14.2.7.2.3	ITT	Summary of Change from Baseline to Week 52 in NPI Total Score By Visit and Treatment Stratified by Mild (20-27)/Moderate (<20) AD Status : Responder Analysis
14.2.8.1	ITT	Summary of Change from Baseline to Week 52 in Zarit Burden Index By Visit and Treatment
14.2.8.2	ITT-mild	Summary of Change from Baseline to Week 52 in Zarit Burden Index By Visit and Treatment
14.2.9.1	ITT	Summary of Change from Baseline to Week 52 in P-tau 217 By Visit and Treatment
14.2.10.1	ITT	Summary of Change from Baseline to Week 52 in GFAP By Visit and Treatment
14.2.11.1	ITT	Summary of Change from Baseline to Week 52 in NfL by Visit and Treatment
14.2.12.1	ITT	Summary of Change from Baseline to Week 52 in Total Tau by Visit and Treatment

Table Number	Population	Table Title/Summary
14.2.13.1	ITT	Summary of Individuals Entering the Study with Mild (MMSE:21-27) Alzheimer's Disease (AD) and Progressed to Moderate (MMSE:16-20) or Severe (MMSE:<16) AD by Week 52
14.2.13.2	ITT	Summary of Individuals Entering the Study with Moderate (MMSE:16-20) Alzheimer's Disease and Progressed to Severe (Moderate:<16) AD by Week 52

